Official Title:	OUR Stress/ Emotion Management for Black/African American Women With Hypertension
NCT Number:	NCT04526145
Document Name:	Study Protocol and Statistical Analysis Plan
Document Date:	October 1, 2021

IRB Protocol Number: 2020B0182
IRB Approval date: 06-28-2020
Version: 11-13-2020
2-23-2024
5-26-2024
10-01-2021

Operating Under Resilience (OUR) Project: Stress and emotion Management for Black/African American Women with Hypertension In a Covid-19 Social Distancing Society

Covid-19 has brought to light the chronic stress of socioeconomic disadvantage experienced by African Americans. Thirty percent of Covid-19 patients are African Americans, despite the fact African Americans make up around 13% of the population in the United States. The body's response to chronic stress results in systemic inflammation and adverse cardiovascular and cognitive health outcomes.^{1,2} Chronic stress is an important risk factor for poor blood pressure control¹ and cognitive decline.³ African American (Black) women are at even greater risk of cognitive decline due to a high prevalence of hypertension, obesity, sleep disturbance, unhealthy eating, and exposure to adversity in the form of discrimination stress.⁴ Emotional dysregulation, as a result of chronic stress, also contributes to cardiovascular disease, anxiety, and depression.⁵⁻⁸ In previous work Co-Created Health Education InterventioN (Co-CHIN) study was created and implemented to promote resilience and healthy behaviors in Black women with hypertension. We collaborated with hypertensive black adults (age ≥ 60) to develop Co-CHIN for hypertension self-care management.⁹⁻¹¹ The Co-CHIN intervention was feasible and acceptable in several ways: We rapidly recruited participants (31 black adults in less than 30 days; 87% women), zero participants dropped out, and 86.7% of participants self-reported that Co-CHIN was applicable to their lifestyle. Ninety-three percent of the women attended all four weekly Co-CHIN sessions. Knowing that lack of physical activity is a risk factor for poor health outcomes, we enhanced Co-CHIN to incorporate physical activity goals into daily routines.

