The purpose of this quasi-experimental pilot study is to determine the feasibility, acceptability, and adherence to a nurse and dietitian-led web-based health education program (eCo-CHIN) to improve stress and emotional regulation in Black women with hypertension. Thirty-two women will be enrolled in 3 cohorts of 6-8.. The feedback from each cohort will be incorporated, in an iterative fashion, to improve delivery of the intervention to the following cohort.

The study aims are to:

Aim 1: Determine the feasibility, acceptability, and adherence to a synchronous web-based health education program, eCo-CHIN, to engage in Covid-19 stress management and BP self-care for Black women with hypertension.

H.1. We hypothesize that the intervention will be feasible, acceptable, and that participants will adhere to eCo-CHIN. Weekly attendance will be recorded. We will use open-ended questions after the 4-week sessions and elicit feedback from participants regarding feasibility and acceptability of eCo-CHIN. A sleep diary, self-reported physical activity, Food Frequency Questionnaire Block, and anthropometric data (weight, BMI, waist circumference) will be collected at baseline, 1 month, and 6 months.

Aim 2: Determine the initial efficacy of eCo-CHIN to reduce stress and improve emotional regulation and BP self-care (BP knowledge, resilience, mindful awareness, diet, sleep hygiene) for Black women with hypertension.

H.2. We hypothesize that there will be an improvement in perceived stress, emotional regulation, and BP self-care from baseline to post-intervention. We will collect psychosocial data using the All of Us Cope COVID-19 survey (which includes sleep, stress , and a resilience scale), Beck Anxiety and Depression measures and surveys of stress, and emotion regulation, , at baseline 1 month, and 6 months.

Aim 3: Explore the feasibility of collecting cognitive performance data (processing speed, attention, and executive function) via teleconference. The Repeatable Neuropsychiatric Battery (RBANS) will be collected at baseline and 6 months. The CAIDE will be assessed at baseline, 1 month and 6 months.

Aim 4: Explore a preliminary economic evaluation of the cost to deliver the intervention over the duration of the study. Research staff will track time and resources needed for implementing the study including personnel, training, facilities, materials, equipment, other inputs, and required client inputs monthly.

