Our preliminary work supports our ability to successfully recruit Blacks and traditionally unheard groups.^{9,10,47} Co-CHIN was created with participants who resided in low-income neighborhoods in Cleveland, Ohio; this makes the Co-CHIN a good candidate for generalizability in low-income areas. Our targeted neighborhoods in Columbus are also low-income neighborhoods. The scientific premise is that the practice of health-promoting self-care behaviors reduces poor nutrition, altered sleep, sedentary behavior, and psychosocial stress and, thereby, reduces negative impacts on the brain, since all these factors contribute to neural inflammation and increased BP.^{14,15} Physiologically, increasing physical activity, managing stress, and eating a healthy diet improve BP and improve cognitive function by decreasing glycemic spikes, triglycerides, cholesterol, and neuroinflammation.¹⁵ Additionally, a lack of social support and a lack of social participation are among the most powerful predictors of morbidity and mortality, even after controlling for relevant lifestyle (e.g., eating, smoking, drinking, exercise) and physical (e.g., increased serum cholesterol and BP) variables. The sharing of BP health information between Black women is associated with greater use of the BP information.⁴⁸ Co-CHIN also uses social interaction, support and mindfulness awareness to promote health behavior change.

Innovation

Through stress management and emotion regulation, our study addresses a recent National Institute on Aging call to action for controlling hypertension in order to prevent sequelae, including mild cognitive impairment, a precursor to ADRD. The proposed study is innovative because we use a culturally informed intervention to impact two of the greatest threats to the health and well-being of Black women: ADRD and hypertension. The eCo-CHIN addresses multiple lifestyle risk factors and harnesses the strength of social support to promote engagement in healthy self-care behaviors during Covid-19. Our study's innovations include:

IRB Protocol Number: 2020B0182
IRB Approval date: 06-28-2020
Version: 11-13-2020
2-23-2024
5-26-2024
10-01-2021

- Maximizing social interaction in a social distancing environment (Covid-19) with peers and health professionals (nurses and dietitians) via a synchronous web-based platform.

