- Cultural tailoring by use of culturally familiar terms in the educational materials, connecting mindful awareness to spirituality, and delivery of sessions in a familiar setting (home).
- The use RBANS via a web-based platform to explore the use of eCo-CHIN to enhance cognitive function (processing speed, attention, and executive function).

III. Procedures/Approach

Introduction. The theoretical framework for our intervention is adapted from the Information-Motivation-Behavioral Skills model.^{49,50} The intervention has three components that include knowledge of basic information regarding an illness/disease (hypertension), motivation through learning in a socially supportive environment (eCo-CHIN), and behavioral skills acquired to manage a chronic illness through improving self-efficacy (confidence in managing hypertension) to cope with stress and support emotional regulation. Demographic, clinical, and lifestyle factors and neurocognitive factors are proposed to influence the adoption of eCo-CHIN, stress management and emotion regulation strategies. Cognitive function is an exploratory feasibility aim to administer testing via teleconference.

A. Research Design

Quasi-experiment pre/post design to test the eCo-CHIN intervention in Black women with hypertension.

The intervention consists of four web-based weekly group sessions, lasting 90 minutes each that are delivered by a Registered Nurse (RN) and a Licensed Dietitian (LD).

B. Sample

Thirty-two Black women age 45-65 (middle-age as defined by the U.S. Census) will be enrolled in 3 cohorts (6-8 participants), with one new cohort beginning every 4-6 weeks. Inclusion criteria are English speaking, self-identification as Black/African American, diagnosis of hypertension (treated with medications and or lifestyle management), female sex, and access to a smart phone or a computer capable of connecting to the Internet (80% of Blacks have a smartphone).⁵¹ Exclusion criteria are no access to computer with internet or Smartphone or diagnosis of resistant hypertension defined as blood pressure that remains above goal despite concurrent use of three antihypertensive agents of different classes, one of which should be a diuretic/water pill.

Measurement/Instrumentation

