Procedures overview. Using an IRB approved script, we will recruit, screen and enroll participants until we have 32 qualified participants. An initial visit will be scheduled to obtain baseline survey data (approximately 90 minutes), and complete the baseline cognitive function testing (60 minutes). Per participant's preference, the survey data and cognitive function testing may be done on two separate days.

Procedures.

Informed consent. Interested participants will be given access to the self-initiating process to provide information (email and phone) and to contact a member of the study team with questions, prior to consent. This will also serve as pre-screening to review inclusion/exclusion criteria for the eligibility of the participants. The eligible participants will be consented using a REDCap-based electronic consent form. The consent form has been developed in REDCap, a secure, web-based, HIPAA-compliant, data collection platform with a user management system allowing project owners to grant and control varying levels of access to data collection instruments or data (e.g. read only, de-identified-only data views). Self-initiating process can be done on personal portable electronic devices using posted QR codes or web-links on study fliers, social media, or websites.

The steps to consenting are as follows:

1. Potential participants would access the Verbal Script for Obtaining Informed Consent The Ohio State University Consent to Participate in Research via REDCap link provided on the study recruitment materials.
2. The consent link will have a prescreen feature.
 - a. If a person says no to one of the inclusion criteria (black/African American, female, diagnosis of hypertension, age 45-65) questions, they would be thanked and told that they do not qualify.

IRB Protocol Number: 2020B0182
IRB Approval date: 06-28-2020
Version: 11-13-2020
2-23-2024
5-26-2024
10-01-2021

- b. This would also be yes for any of the exclusion criteria (no access to computer with internet or Smartphone, diagnosis of resistant hypertension defined as blood pressure that remains above goal despite concurrent use of three antihypertensive agents of different classes, one of which should be a diuretic/water pill).
 - c. If the person meets the eligibility criteria, then the verbal script for obtaining informed consent will appear.
 3. At the end of the consent form, the person would click a checkbox to be enrolled in the study.

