For Aim 2, we will first use descriptive statistics and trend plots to examine the outcomes (stress and emotional regulation) over time (baseline, 1-month, and 6-months). Next, Paired T-tests will be performed to examine the change of each outcome at 1-month (vs. baseline) and at 6-months (vs. baseline). Sample size from this pilot study will not have sufficient power to detect small-to-medium effect sizes for within-group difference (e.g., 54% power to detect a Cohen’s d of 0.5 with a two-sided significance level of 0.05). Therefore, we will not rely on statistical significance. Instead, we will estimate point estimates, 95% confidence intervals and effect sizes. These estimates along with clinical significance will guide our results interpretation and inform the sample size determination for a future NIH funding mechanism. For Aim 3, changes in RBANDS measure will be analyzed using the same approach for Aim 2 (baseline and 6 months). For Aim 4, Co-I [name], Health Economist, will use descriptive statistics, trends, and plots to evaluate allocations of resources and estimate costs of the intervention at various stages.

F. Project Timeline

The development of this group-delivered intervention will be an iterative process, and we will use this pilot data to submit an external grant for a 12-week intervention through the National Institutes on Aging in 12-18 months.

Table 2. Project timeline.

Activity	1-2 months	3-4 months		5-6 months	7-8 months	9-10 months	11-12 months
IRB application	X						
Recruitment		X		X			
Data collection (baseline, 1-month, 6-months)		X		X	X	X	
Delivery of Intervention		X		X	X		
Preliminary data analysis of baseline data for an NIH grant in February 2022				X	X	X	X
Final data analysis						X	X
Dissemination							X

IRB Protocol Number: 2020B0182
IRB Approval date: 06-28-2020
Version: 11-13-2020
2-23-2024
5-26-2024
10-01-2021

References

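### The planned 32 women do not fit in 3 cohorts of 6-8, and the stated 54% power does not match 32 women

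*Combined protocol and SAP*

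**What the plan says.** **Enrolment.** Section I (Objectives) says "Thirty-two women will be enrolled in 3 cohorts of 6-8". Section III.B (Sample) repeats it: 32 women "will be enrolled in 3 cohorts (6-8 participants), with one new cohort beginning every 4-6 weeks". The Procedures overview says "we will recruit, screen and enroll participants until we have 32 qualified participants".

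**Analysis and power.** For Aim 2, section III.E (Data Analysis) says "Paired T-tests will be performed to examine the change of each outcome at 1-month (vs. baseline) and at 6-months (vs. baseline". It then says that the pilot cannot detect small-to-medium within-group effects and gives as its example 54% power at d = 0.5 with a two-sided 0.05 level. From this it concludes that it will not rely on significance. It will report point estimates, 95% confidence intervals and effect sizes, which are also to inform the sample size of a later study. The power sentence names no n, no attrition rate and no SD for d.

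**Delivery.** Sessions are given to groups, and section I adds: "The feedback from each cohort will be incorporated, in an iterative fashion, to improve delivery of the intervention to the following cohort". Data Analysis does not mention cohorts.

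**The concern.** Two pairs of statements do not agree: 32 women against 3 cohorts of 6-8, and 32 women against 54% power. A reader cannot tell how many women will be enrolled, in how many groups, or how many are expected in the analysis.

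The power figure has a job to do, because the decision to set significance aside is drawn from it. The estimates and intervals then become the main Aim 2 output and feed the design of the next study, so their expected precision should be known in advance. That precision depends on the n that the plan leaves open.

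**Working it through.** **Inputs from the documents.** Enrolment 32 (sections I and III.B, Procedures overview); 3 cohorts of 6-8 (sections I and III.B); paired t-test, d = 0.5, two-sided 0.05, stated power 54% (section III.E).

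**Step 1: cohorts.** 3 × 6 = 18 and 3 × 8 = 24, so three cohorts of the stated size hold 18 to 24 women. Reaching 32 takes four cohorts of 8 (4 × 8 = 32), five of 6 or 7 (3 × 6 + 2 × 7 = 32), or three of about 11 (32/3 = 10.7).

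**Step 2: the plan's power figure.** Assume that d is the mean change divided by the SD of change. Power is then P(|T| > t crit), where T is noncentral t with n − 1 degrees of freedom and noncentrality d√n. The expected half-width of the 95% CI, in SDs of change, is t crit/√n.

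| n | 0.5√n | t crit | Power | CI half-width |
|---|---|---|---|---|
| 18 | 2.121 | 2.110 | 51.6% | 0.50 |
| 19 | 2.179 | 2.101 | 54.1% | 0.48 |
| 20 | 2.236 | 2.093 | 56.5% | 0.47 |
| 24 | 2.449 | 2.069 | 65.0% | 0.42 |
| 32 | 2.828 | 2.040 | 78.2% | 0.36 |

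The 54% is not reproduced at 32, 24 or 18. On this definition of d it is reproduced at n = 19.

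**Step 3: what could lie behind the 54%.**

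- *Attrition.* 19 completers is 1 − 19/24 = 20.8% lost from 24, or 1 − 19/32 = 40.6% lost from 32.
- *A different SD.* If d is standardised by the raw SD (equal at both times) and the pre/post correlation is ρ, the effect in SDs of change is 0.5/√(2(1 − ρ)). At ρ = 0.35 this is 0.5/√1.30 = 0.439, which gives 54% at n = 24. At ρ = 0.12 it is 0.5/√1.76 = 0.377, which gives 54% at n = 32.
- *A normal approximation* gives 54.1% at n = 17, which is below the 18 that three cohorts of 6 would hold, so it too would need unstated losses.
- *A level of 0.01* gives 54.0% at n = 32, but the plan states 0.05.

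The first two are possible, but the plan states neither an attrition rate nor a correlation.

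**The case against.** **The figures may be compatible.** 19 lies inside 18-24 and equals 24 less about 20%, so the cohort plan and the 54% can be squared. This stands: a reader might infer a three-way contradiction, but the two firm conflicts are 32 against the cohorts and 32 against 54%. The match to n = 19 also depends on how d is standardised, which the plan does not say, so it does not show that the power was miscalculated.

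**The earlier study.** A reader might argue that losses are ruled out because in the earlier study "zero participants dropped out". That is weak evidence. The account of that study mentions only four weekly sessions, whereas this one runs remotely to 6 months and treats attrition as something to be measured.

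**It is a pilot.** The primary outcome is feasibility and acceptability, and not relying on significance is defensible on that ground alone. This limits the consequence but leaves the figures unreconciled.

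**A stronger reading about clustering.** Peer support is an intended mechanism: the intervention "harnesses the strength of social support to promote engagement in healthy self-care behaviors during Covid-19" and works through "motivation through learning in a socially supportive environment (eCo-CHIN". A reader might infer that the paired-t intervals are too narrow because women in a group resemble one another, or that the pooled mean hides drift as delivery is revised. The documents do not establish either. They give no within-cohort correlation, do not say that the intervals are meant to apply to new groups, and give no size for any effect of revising delivery. Any figure for lost coverage or drift would come from assumed values. What remains is an unstated assumption of independence.

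**Conclusion.** Wrong as written. The enrolment of 32 cannot be met by 3 cohorts of 6-8, which fall short by 8 to 14 women (32 − 24 and 32 − 18). This needs no assumption. The 54% does not describe 32 analysed women if d is in SDs of change: the figure there is 78.2%, about 24 points higher. That second statement rests on the definition of d, and an unstated attrition rate or correlation could explain the gap.

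The consequence is moderate. At n = 32 the plan's own example no longer supports its power argument as stated, and the expected interval is about a quarter narrower than at n = 19 (0.36 against 0.48 SD; 0.36/0.48 = 0.75). The choice to emphasise estimation can stand.

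The documents do not support a finding that the paired t-test is invalid or that its intervals under-cover because of group delivery. That matter warrants at most a caveat.

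**What to change.** 1. Reconcile 32 women with the number and size of cohorts, using the same wording in sections I and III.B and the Procedures overview.
2. In section III.E, state the n expected in the analysis at 1 and 6 months, any attrition assumed, and which SD standardises d.
3. Restate the power for that n (about 78% if 32 are analysed and d is in SDs of change), and give the expected CI half-width beside it, since the interval is what will be used.

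Optional: add a sentence saying that the paired-t intervals assume independence between women although delivery is in groups and is revised between cohorts, and list mean change by cohort as description only. The table should carry a warning that cohorts of 6-8 are too small to detect drift. The 95% half-width for one cohort's mean is 2.571/√6 = 1.05 SD to 2.365/√8 = 0.84 SD. For the difference between two cohorts it is 2.228 × √(2/6) = 1.29 SD to 2.145 × √(2/8) = 1.07 SD.

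The cost is a few lines of text and, if the option is taken, one small table. If the reconciliation leads to more or larger cohorts, the project timeline needs checking as well. The paired t-tests do not need to change.

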Recruitment. Participant recruitment will be through advertisement at local primary care clinics, Family Medicine's Research Network, ResearchMatch, churches, and community organizations with flyers and online social networks (e.g. websites, Facebook, LinkedIn). Participants may self-refer or be referred by a provider. All recruitment efforts will begin once approval from the IRB is received. The primary recruitment in the proposed study is ResearchMatch (attached Guidance and Message Template for IRB Submission for Use of ResearchMatch.org). I am requesting the use of ResearchMatch.org for participant recruitment on this protocol. In addition, we will use other social media because as many as 68% of adults in the US use Facebook regularly. Permission from the appropriate party (e.g. moderator of Facebook page) will be gained prior to the posting of any recruitment materials. Once approval is received, the study team will post a flyer (see attachment) in each respective online location. The flyer contains general information about the study including university affiliation, time commitment, confidentiality, compensation availability, and contact information for eligibility and screening procedures. We will also provide recruitment information to the Women's Place at The Ohio State University. We will also use snowball recruiting where participants inform their contacts about the study to enable their contacts to potentially be enrolled in the study.

Participant ID: Participants will be assigned a REDCap auto-generated ID number which will identify them at all data collection points.

Retention Plans.

In studies longitudinal studies, a threat to internal validity is selection bias or selection threat. This can occur due to study drop out. To decrease the risk of participants dropping out of the study, we have employed several strategies.

1. Data collection and intervention delivery option for weekends and evenings.
2. Reminder calls to participants for data collection and sessions.
3. Participants will be remunerated for their assessment time according to the following schedule:

After completion of the COVID ALL OF US COPE survey at baseline, you will receive a \$10.00 Amazon gift card.

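### The Aim 2 paired t-tests use only women seen at both visits, and no missing-data method stands beside them; a mixed model on all visits should be the main estimate, with the paired results shown next to it (minor)

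*Combined protocol and SAP*

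**What the plan says.** The study is a single-group design (III.A Research Design): "Quasi-experiment pre/post design to test the eCo-CHIN intervention in Black women with hypertension". The enrolment target is 32 (Procedures overview): "recruit, screen and enroll participants until we have 32 qualified participants".

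Under III.E Data Analysis, Aim 2 begins with descriptive statistics and plots to "examine the outcomes (stress and emotional regulation) over time (baseline, 1-month, and 6-months". Then "Paired T-tests will be performed to examine the change of each outcome at 1-month (vs. baseline) and at 6-months (vs. baseline". The section gives up reliance on significance. It rests interpretation on point estimates, 95% confidence intervals and effect sizes, which are also to inform the size of a future trial. Aim 3 applies the same approach to RBANS, measured at baseline and 6 months only.

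On dropout, Retention Plans says that in longitudinal work "a threat to internal validity is selection bias or selection threat". It answers this with flexible scheduling, reminder calls and remuneration, and has the reasons for withdrawal recorded. Data Analysis reports attrition as a feasibility rate under Aim 1. The documents give no expected dropout rate, missing-data method, mixed model or sensitivity analysis. Withdrawn women are to complete a discharge visit, but its content is not described, so it cannot be counted as a source of outcome data.

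**The concern.** A paired t-test drops every woman who lacks one of its two visits. The 1-month and 6-month changes may therefore come from different sets of women, and an apparent fading or persistence of effect could partly be a change of sample. A woman who leaves after 1 month contributes nothing to the 6-month estimate, although two of her scores are known.

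If the women who leave began with higher stress, or had responded poorly by 1 month, the completers' mean change is not the mean change of those enrolled. The plan asks readers to rely on the estimates rather than on p-values, so bias in the estimate matters more than loss of power. The confidence interval shows sampling error but not this bias.

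**Working it through.** **The plan's own figure.** The plan gives "54% power to detect a Cohen’s d of 0.5" "with a two-sided significance level of 0.05". Paired t-test power from the noncentral t (df = n − 1, noncentrality 0.5√n) is:
- n = 32: 78.2%
- n = 24: 65.0%
- n = 19: 54.1%
- n = 18: 51.6%

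The stated figure fits 19 pairs, not 32. That is a separate point. Here it shows only that the number of completing pairs the plan expects is not stated.

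**Inputs for the bias.** From the documents: three visits, 32 women, paired change. Assumed: visit SD 1, equal visit correlations ρ = 0.5, 20% lost before 6 months, and log-odds of dropout rising by ln 2 per SD of a driver S.

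**Formulas.** Let δ be the mean of S, in SD units, among completers.
- Paired bias = δ × Cov(Y6 − Y0, S) / SD(S).
- A likelihood model on all visits in effect predicts the missing Y6 from Y0 and Y1, each with slope ρ/(1 + ρ) = 1/3. Its bias is approximately δ × Cov(Y6 − (Y0 + Y1)/3, S) / SD(S).

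When S is the 6-month change itself (SD 1), the paired bias equals δ. Simulation of 600,000 women gave −0.128, so δ = −0.128.

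| Dropout driven by | Paired: factor, bias | All-visits model: factor, bias |
|---|---|---|
| Baseline score | −0.5, +0.064 | 0, 0 |
| 1-month change | 0.5, −0.064 | 0, 0 |
| 1-month value | 0, 0 | 0, 0 |
| Stable unobserved level | 0, 0 | 0.236, −0.030 |
| Unseen 6-month value | 0.5, −0.064 | 0.667, −0.085 |
| Unseen 6-month change | 1, −0.128 | 0.667, −0.085 |

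For the stable level, Cov = 0.5 × (1 − 2/3) = 0.167 and SD = √0.5 = 0.707, so the factor is 0.167/0.707 = 0.236. Simulated values agree with the table: +0.063 (paired, baseline), −0.065 (paired, 1-month change) and −0.088 (model, 6-month change).

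**Range.** With 20-30% dropout, odds ratio 2-3 per SD and correlations 0.5-0.6:
- Dropout on baseline: paired bias +0.05 to +0.14 SD; model about 0.
- Dropout on poor 1-month response: paired bias −0.06 to −0.15 SD; model about 0.
- Dropout on a stable unobserved level: paired about 0; model −0.03 to −0.07 SD.

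**Small samples.** 1,000 simulated trials per setting, true change −0.5 SD, correlation 0.5, about 20% dropout, odds ratio 2:

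| n | Driver | Paired mean (RMSE) | Model mean (RMSE) |
|---|---|---|---|
| 32 | Baseline | −0.447 (0.207) | −0.510 (0.201) |
| 32 | 1-month change | −0.565 (0.208) | −0.500 (0.196) |
| 19 | Baseline | −0.434 (0.262) | −0.499 (0.260) |
| 19 | 1-month change | −0.565 (0.264) | −0.506 (0.259) |

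The 95% intervals are 0.77-0.81 SD wide at n = 32 and 1.04-1.09 SD at n = 19. Across these four settings, model coverage is 92.0-94.2% with a normal critical value and 94.1-95.3% with t on completers minus 1 df. Kenward-Roger itself was not simulated. With no dropout the two estimates are identical.

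**Consequence for sizing.** If the next trial were sized directly on this change with the SD held fixed, n would scale with 1/effect². For a true −0.5 SD, an estimate of −0.565 gives (0.5/0.565)² = 0.78, about 22% too few. An estimate of −0.437 gives (0.5/0.437)² = 1.31, about 31% too many.

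**The case against.** The strongest reply is that the model does not dominate the paired test. Chronically stressed women may be the ones who leave. If dropout follows a stable unobserved level, that level cancels in a woman's own difference, so the paired change is unbiased and the model is not. Dropout on the unseen 6-month value also favours the paired test slightly. A reader might infer that missing at random is a weaker assumption than the paired test needs. It is not: neither assumption contains the other. This stands in full, and it is why the paired results should be kept.

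A reader might also infer that the model removes dropout bias at no cost. If dropout follows the unseen 6-month change, 0.088/0.128 = 69% of the paired bias remains in the base case. The model also adds distributional and covariance assumptions and needs a small-sample df correction.

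Third, every size above is assumed. The only dropout figure in the documents is zero, from an earlier four-session study. That says little about 6-month follow-up, but nothing in the documents shows that dropout will be substantial or of a given kind. The two mechanisms that bias the paired test push in opposite directions, and dropout on the 1-month value alone gives no bias.

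Finally, this is an uncontrolled feasibility pilot, Aim 2 is initial efficacy, and the plan does act on retention and report attrition. To say that it ignores dropout would be wrong. The gap is in how Aim 2 is estimated.

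**Conclusion.** The point holds as a minor one. The Aim 2 estimates rest on completers only, discard known 1-month scores and have no missing-data method beside them, although the plan names the threat. Under dropout related to observed baseline stress or early response, the bias is roughly 0.05-0.15 SD in either direction, given 20-30% dropout, an odds ratio of 2-3 per SD and correlations of 0.5-0.6. The base-case bias of 0.064 SD is about 8% of a 0.8 SD interval at n = 32. The paired RMSE is 3-6% higher there (0.207/0.201 and 0.208/0.196) and 1-2% higher at n = 19.

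Two stronger readings are not supported. The documents do not show that the 6-month estimate will be biased, or in which direction. Nor can 19 pairs be read as a planned dropout of 41% from 32, or 21% from the 24 that "Thirty-two women will be enrolled in 3 cohorts of 6-8" would allow at most, because neither rate is stated.

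**What to change.** In III.E Data Analysis:

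1. Make the main Aim 2 estimate for each outcome a likelihood-based mixed model on all available visits from all enrolled women: visit as a three-level factor, unstructured covariance, REML, Kenward-Roger df. Report the 1-month and 6-month contrasts with 95% confidence intervals. A classical repeated-measures ANOVA would not serve, because it also deletes incomplete women.
2. Report the paired completer results beside it, with the number of pairs at each visit, and explain any difference.
3. Compare the baseline and 1-month scores of completers and non-completers at 6 months.
4. Add a simple sensitivity analysis that shifts the unseen 6-month scores over a stated range.
5. For RBANS, state that with no 1-month score a model can correct only for baseline-related dropout.

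The cost is a short paragraph in the plan, slightly more analysis work, and added model assumptions in a small sample. No extra data are needed.
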